Exercise status ^q	Х	Х	Х	Х	Х	Х	Х	Х	Х	Х	Х	Х
Adverse event assessment	Х	Х	Х	Х	Х	Х	Х	Х	Х	Х	Х	Х

5XSTS: 5 time sit to stand; 6MWT: 6-minute walk test; ALDOA: aldolase A; CK: creatine kinase; C-SSRS: Columbia-Suicide Severity Rating Scale; CYC: cytochrome c; ECG: electrocardiogram; EOS: end of study; EOT_P2: end of treatment during double-blind treatment period; EQ-5D-5L: European Quality of Life 5-dimension, 5-level

24 Jan 2024 *Footnotes* Version 9.0 Substantial Amendment 8

- CONFIDENTIAL -

questionnaire; FLNC: filamin-C; IP: investigational product; MB: isoenzymes found in heart muscle; MFIS: Modified Fatigue Impact Scale; MM: isoenzymes found in skeletal and heart muscle; Neuro-QoL: Quality of Life in Neurological Disorders; PGIC: Patient Global Impression of Change; PGIS: Patient Global Impression of Severity; PPARδ: peroxisome proliferator-activated receptor delta; QTcF: QT interval using Fridericia's correction; WOCBP: women of childbearing potential

- a. All assessments at the study site visit may be performed over 2 to 3 days. Assessments scheduled for each study site visit should be completed within visit window.
- b. The site will perform follow-up phone call visits. Blood sample collection and ECG will be performed by qualified healthcare provider from the home healthcare vendor (ECG will be performed at weeks 2 and 8 only). In case the home healthcare visit is not feasible, the visit can be conducted at the study site.
- c. IP administration should be started after the completion of assessments at week 0, except for postdose blood sampling for pharmacokinetics. The day participants start taking the IP is considered as day 1.
- d. Participants who discontinue the study treatment will visit the site and perform EOT_P2 assessments. Participants will be encouraged to visit the study site for EOT_P2 assessments as soon as the discontinuation of the study treatment. Participants who discontinue the study will be followed until the EOS visit. Participants who remain in the study for efficacy and safety evaluations will continue to follow the schedule of assessments without IP dosing.
- e. To be performed prior to randomization.
- f. Vital signs will be taken prior to blood draw. Blood pressure and pulse will be measured in the sitting or supine position after the participant has rested for at least 5 minutes.

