7.2.7 Columbia-Suicide Severity Rating Scale

- The C-SSRS was developed as a screening tool to identify suicide risk. The interviewer asks participants detailed questions regarding suicidal ideation, behaviors, intensity of ideation and attempts. Response options and recall periods vary in accordance with the nature of the question.
- The C-SSRS will be performed by trained site staff via interview as outlined in the schedule of assessments [Table 1]. At screening, the "Screening" version is to be used to determine eligibility. During all subsequent visits, the "Since Last Visit" version is used to monitor on study suicidal ideation and behavior after the initial assessment. If possible, continuity of raters should be maintained across visits for each participant.
- Participant who has a history of suicide attempt, suicidal behavior or has any suicidal ideation within 1 year prior to screening that meets criteria at a level of 4 or 5 by using the C-SSRS or who is at significant risk to commit suicide, as assessed by the investigator at screening will be excluded.

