5.4.7 Columbia-Suicide Severity Rating Scale (C-SSRS)

The C-SSRS will be performed by trained site staff via interview at screening, randomization, and all subsequent study visits. At screening, the "Screening" version is to be

used to determine eligibility. During all subsequent visits, the "Since Last Visit" version is used to monitor on study suicidal ideation and behavior after the initial assessment. If possible, continuity of raters should be maintained across visits for each patient. The following five questions regarding suicidal ideation, six questions regarding suicidal behavior and question for non-suicidal self-injurious behavior will be used for analysis.

- Suicidal Ideation ('Yes' to any one of the below 5 questions for suicidal ideation)
 - Wish to be Dead (No/Yes)
 - o Non-Specific Active Suicidal Thoughts (No/Yes)
 - Active Suicidal Ideation with Any Methods (Not Plan) without Intent to Act (No/Yes)
 - o Active Suicidal Ideation with Some Intent to Act, without Specific Plan (No/Yes)
 - o Active Suicidal Ideation with Specific Plan and Intent (No/Yes)
- Suicidal Behavior ('Yes' to any one of the below 5 questions for suicidal behavior)
- Preparatory Acts or Behavior (No/Yes)
 - Aborted Attempt (No/Yes)
 - Interrupted Attempt (No/Yes)
 - Actual Attempt (No/Yes)
 - o Completed Suicide (No/Yes)
- Suicidal Ideation or Behavior ('Yes' to any one of the above 10 questions for suicidal ideation and behavior)
- Self-injurious Behavior Without Suicidal Intent (No/Yes)

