6.5.5.2 C-SSRS

The results of five questions regarding suicidal ideation, six questions regarding suicidal behavior, suicidal ideation or behavior and self-injurious behavior without suicidal intent will be summarized using number and percent of participants by analysis group at each visit. For

all analysis visits, the data "by the last dose + 7 days" and the data before the first dose date of open label extension part will be included.

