6.8 Additional Conventions

6.8.1 Analysis Windows

Day 1 and Day -1 are defined as the day of start taking the IP and its prior day, respectively.

The following analysis window will be used.

The data summary by visits will be done following the analysis windows specified in the table below:

Analysis Visits	Scheduled Day in	Analysis Windows (day)
	Protocol	
Screening	Day -28	-35 to -14
Week 0 (Baseline)	Day -2 to 1	-2 to 1
Week 1	Day 8	5 to 13
Week 2	Day 14	14 to 18
Week 3	Day 22	19 to 25
Week 4	Day 29	26 to 42
Week 8	Day 57	43 to 70
Week 12	Day 85	71 to 98
Week 16	Day 113	99 to 126
Week 20	Day 141	127 to 154
Week 24	Day 169	155 to 182
Week 28	Day 197	183 to 210
Week 32	Day 225	211 to 238
Week 36	Day 253	239 to 266
Week 40	Day 281	267 to 294
Week 44	Day 309	295 to 322
Week 48	Day 337	323 to 350
Week 52	Day 365	351 to 378
End of Double Blind Part	Day 365	2 to 378
Follow-up	The last dose + 28	The last dose + 28 days to the last dose +
-	days	35 days

For the analyses of safety and efficacy, for all analysis visits excluding follow-up visit, the data "by the last dose + 7 days" and the data before the first dose date of open label extension part will be included.

If more than one observation exists within the analysis window, the observation closest to the scheduled visit day will be selected for that visit. If there are two observations that have the same distance from the scheduled day, the value that is after the scheduled day will be selected in the analysis. If more than one observation is made on the same day, an average value if continuous or the worst value if categorical will be included in the analysis.

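### The by-visit C-SSRS tables can lose a positive answer altogether, because the closest-to-schedule rule discards interviews that each cover a different interval

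*SAP*

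**What the plan says.** On recall period, Protocol 7.2.7 states: "During all subsequent visits, the 'Since Last Visit' version is used to monitor on study suicidal ideation and behavior". Section 5.4.7 of the 52-week SAP and section 5.2.7 of the 76-week SAP repeat this.

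On analysis, 52-week SAP 6.5.5.2 has the C-SSRS results "summarized using number and percent of participants by analysis group at each visit". It restricts them to data up to last dose + 7 days and before the first OLE dose. The 76-week SAP 6.5.5.2 also tabulates by visit. Neither SAP plans a row for a positive answer at any time on treatment.

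On selection, 52-week SAP 6.8.1 states: "If more than one observation exists within the analysis window, the observation closest to the scheduled visit day will be selected for that visit". Equal distances go to the later record. Only when several records fall on the same day does the plan take "an average value if continuous or the worst value if categorical will be included in the analysis". The 76-week SAP 6.8.1 has the same rules.

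The window table also has an end-of-part row, "End of Double Blind Part Day 365 2 to 378" (analysis visit, target day, window). The 76-week counterpart is End of Treatment, Day 533, Days 2 to 560.

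On early stopping, Protocol Table 1 footnote d states: "Participants who discontinue the study treatment will visit the site and perform EOT_P2 assessments".

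**The concern.** Keeping the record nearest the target day is sensible for a repeated measurement of a current state, such as blood pressure, where two readings in a window are near substitutes. Interviews with the *Since Last Visit* form are not substitutes. Each covers its own interval, and the next one does not ask about that interval again. Discarding an interview discards its interval.

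C-SSRS is listed under the primary safety objective. If a Yes can be dropped from the week row and is not picked up by the end-of-part row, the placebo-controlled table understates the number of participants with suicidal ideation or behaviour. In arms this small a single participant is visible in the result.

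**Working it through.** The plan states no figure to reproduce. The check applies the 6.8.1 rule to pairs of interview days.

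**Inputs from 52-week SAP 6.8.1**
- Week 12: target Day 85, window Days 71–98. Week 24: target 169, window 155–182. Week 36: target 253, window 239–266. Each window is 28 days wide.
- End of Double Blind Part: target Day 365, window Days 2–378.
- Rule: smallest |day − target|; ties to the later day; worst value only on the same day.
- Eligible: day ≤ last dose + 7, before the first OLE dose.

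**Assumptions**
- The scheduled interview is within ±3 days of target (the visit window in Protocol Table 1).
- The second interview is on another day in the same window.
- For the counts, end of treatment (EOT) is on the day of last dose.

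**(a) Scheduled Yes, then EOT No.** Take Day 82 Yes, last dose Day 82, EOT Day 86 No. Both are eligible (82 + 7 = 89).
- Week 12: |82 − 85| = 3 and |86 − 85| = 1, so Day 86 (No) is kept.
- End of Double Blind Part: |82 − 365| = 283 and |86 − 365| = 279, so Day 86 (No) is kept.
- The Yes is in no row. The Day 86 interview asked only about the time since Day 82.
- A tie also loses it: with Day 83 Yes and Day 87 No, both are 2 days from target and the later is taken.

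Count for Week 12: scheduled day 82 to 88, EOT any later day to 98, gives 16 + 15 + 14 + 13 + 12 + 11 + 10 = 91 pairs. The Yes is displaced when |EOT − 85| ≤ |scheduled − 85|. That is 6 EOT days for Day 82 (83–88), 4 for Day 83 (84–87), 2 for Day 84 (85–86) and none from Day 85 on: **12 of 91**. Weeks 24 and 36 give the same counts.

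**(b) Unscheduled Yes, participant continues.** Take Day 85 No, Day 92 Yes, then No at Days 169, 253 and 365.
- Week 12: distances 0 and 7, so Day 85 (No) is kept.
- End of Double Blind Part: Day 365 (No) is kept.
- The Yes is in no row.

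Count: 7 scheduled days × 27 other days = 189 pairs. The unscheduled record is kept in 6 + 4 + 2 + 0 + 1 + 3 + 5 = 21 (scheduled day 82 to 88 in order), so the Yes is lost from every row in 189 − 21 = **168 of 189**. An unscheduled Yes in a window with no scheduled C-SSRS, such as Day 57 in the Week 8 window (43–70), is kept.

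**(c) Scheduled No, then EOT Yes.** Take Day 85 No, last dose Day 91, EOT Day 92 Yes.
- Week 12 keeps Day 85 (No).
- End of Double Blind Part: |85 − 365| = 280 and |92 − 365| = 273, so Day 92 (Yes) is kept.
- Over the 91 pairs, the Yes leaves the week row in 91 − 12 = 79 but is absent from all rows in **0 of 91**.

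**(d) Any-Yes scoring.** If a window is Yes whenever any eligible interview in it is Yes, losses in (a) and (b) fall to 0 of 91 and 0 of 189.

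These are counts of day pairs. They are not event probabilities.

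**Effect of one lost positive.** With 33 interim participants split evenly over 3 arms (an assumption), 1/11 = 9.1 percentage points. At the planned 22 per arm, 1/22 = 4.5.

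**Item count.** 52-week SAP 5.4.7 announces six suicidal-behaviour questions, lists five, and builds the ideation-or-behaviour composite on 10 questions (5 + 5). Section 6.5.5.2 again says six. Sections 5.2.7 and 6.5.5.2 of the 76-week SAP repeat the mismatch.

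**The case against.** A reader might infer that a positive EOT interview shortly after a negative scheduled one is lost. The documents do not support that. Case (c) shows that the end-of-part row picks it up for anyone stopping before Day 365, provided it falls within last dose + 7 days. A later EOT positive is excluded by that cut-off, not by the closest-day rule.

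What remains is narrower and may be rare. Case (b) needs an ad hoc interview, and neither Protocol Table 1 nor 7.2.7 schedules one. Case (a) needs an EOT interview as near to the target day as the scheduled one, or nearer. The EOT instruction is read from Protocol version 9.0, whereas the SAP says all participants took part under version 7.0 or earlier, whose visit schedule is not available here. Nothing shows that two interviews often share a window.

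Serious positives also have other routes to visibility. Protocol 8.1 lists a level 4 or 5 answer among the reasons for stopping IP, and the SAP tabulates treatment discontinuation by reason and TEAEs. The TLF specifications, not among the documents, may include a C-SSRS listing.

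All of this stands as a limit on likelihood, but it does not remove the defect. Case (a) uses only interviews that the protocol text requires. Ideation at levels 1 to 3 counts in the SAP composite but does not meet the 8.1 criterion, so it may leave no trace elsewhere. Protocol 9.4.3.7 promises only a summary for C-SSRS, while the neighbouring sections on laboratory, vital-sign, weight, ECG and echocardiogram data promise listings.

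One caution applies to the remedy. An any-time row without a cut-off would count events after placebo participants switch to ASP0367 under placebo.

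**Conclusion.** The selection rule does not suit a since-last-visit instrument, and as written it can remove a positive C-SSRS answer from every planned row. The loss is confined to two cases: a scheduled positive displaced by a negative EOT interview nearer the target day, and an unscheduled positive in a participant who continues and shares a window with a scheduled interview. The documents give no basis for a frequency. The cost of one occurrence is about 9 percentage points in an arm of 11, or 4.5 in an arm of 22.

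The conclusion assumes that 6.8.1 applies to C-SSRS as written and that EOT interviews were done under the version in force. The six-versus-five mismatch is a separate, editorial error that begins inside 5.4.7.

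**What to change.** In section 6.5.5.2 of both SAPs:

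1. Exempt C-SSRS from the closest-value rule. Score an item Yes for a window if any eligible interview in that window is Yes.
2. Add one row per item and per composite, by analysis group, for Yes at any time on treatment. Keep the existing limits. In the 52-week SAP: after first dose, up to last dose + 7 days, and before the first OLE dose. In the 76-week SAP: after first ASP0367 dose, up to last dose + 7 days.
3. Reconcile the suicidal-behaviour items, so that the stated number, the list and the composite agree between 5.4.7 (5.2.7 in the 76-week SAP) and 6.5.5.2.

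The cost is SAP wording and a small amount of extra derivation and table work. No new data are needed.

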6.8.2 Imputation Rules for Incomplete Dates

For AEs, a missing or incomplete onset date will be imputed according to the following conventions.

If an onset date is missing, the imputed onset date will be the date of first dose of study drug.

If only the year is known for the AE onset date, the imputed onset date will be the latest of the following non-missing dates:

- Date of first dose of study drug
- January 1 of the year of AE onset date

If only the month and year is known for the onset date, set the surrogate onset date to the first day of that month and then apply the following rules.

- If the month and year of the onset date is prior to the month and year of the first dose of study drug, then the surrogate onset date will be the imputed onset date.
- If the month and year of the onset date is on or after the month and year of the first dose of study drug, then the imputed onset date will be the latest of the following non-missing dates:
- Date of first dose of study drug
- Surrogate onset date
- If the imputed onset date is after the AE end date, the imputed onset date will be the same as the AE end date.

For duration of disease of primary diagnosis, a missing or incomplete diagnosis date will be imputed according to the following conventions.

If a diagnosis date is missing, the diagnosis date will not be imputed. The duration of disease in baseline analysis will be treated as missing data.

If only the year is known for the diagnosis date, the imputed diagnosis date will be January 1 of the year of the diagnosis date.

If only the month and year is known for the diagnosis date, set the imputed diagnosis date will be the first day of that month.

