9.5 Additional Conventions

If the start and stop dates of AEs and concomitant medications are incomplete, imputed dates will be used to determine whether an AE is/is not treatment emergent or to allocate a concomitant medication to the study period it was taken.

Refer to the SAPs for details of the definition for analysis windows to be used for analyses by visit.

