5.4 Primary Safety Endpoints

5.4.1 Treatment Emergent Adverse Events (TEAEs)

AE collection begins after the ICF has been signed and continues until the follow up visit or 28 days after the final IP administration or when the participant is determined to be a screen failure. A TEAE is defined as an AE observed after starting administration of the IP to 28 days after the last dose of IP for double-blind treatment period of the study or moving to the OLE part, whichever comes first.

An IP-related TEAE is defined as any TEAE with a causal relationship of "yes" by the investigator.

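### When only the onset year is known and it precedes the first-dose year, SAP 6.8.2 dates the AE to first dose, so a pre-treatment event is classed as treatment-emergent

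*SAP*

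**What the plan says.** The 52-week SAP, section 6.8.2, handles incomplete AE onset dates in three tiers.

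- **Onset wholly missing:** use the date of first dose.
- **Year only:** "If only the year is known for the AE onset date, the imputed onset date will be the latest of the following" dates, namely first dose of study drug and "January 1 of the year of AE onset date". There is no separate branch for an onset year before the first-dose year.
- **Month and year:** first set a surrogate date on day 1 of the month. If that month is "prior to the month and year of the first dose of study drug, then the surrogate onset date will be the imputed onset date". Otherwise take the later of first dose and the surrogate.

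An end-date check is printed as the last bullet of the month-and-year tier: "If the imputed onset date is after the AE end date, the imputed onset date will be the same as the AE end date". Its wording is general, but its position leaves unclear whether it also covers year-only dates.

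Section 6.8.2 of the 76-week SAP repeats all of this.

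The imputed date has a defined use. Protocol 9.5 says that "imputed dates will be used to determine whether an AE is/is not treatment emergent". In the 52-week SAP, section 5.4.1, "A TEAE is defined as an AE observed after starting administration of the IP to 28 days after the last dose of IP" in the double-blind period (or the move to the OLE, if earlier). Pre-dose events are in the data, because "AE collection begins after the ICF has been signed and continues until the follow up visit".

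**The concern.** Imputing to first dose is a sensible cautious choice when the recorded information cannot say whether an event began before or after treatment. That is the position when the onset year equals the first-dose year. It is not the position when the recorded year is earlier, because the year alone then shows that the event began before treatment. The year-only rule overrides that information, while the month-and-year rule beside it respects it. Two records that both place the onset before treatment are therefore classified differently, and the only difference is whether the month was written down.

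What is at stake is the accuracy of the TEAE tables in section 6.5.1, which are built on the treatment-emergent flag.

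**Working it through.** The documents give no figure to reproduce. The check applies the rules as written.

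**Inputs.** The year-only rule, month-and-year rule and end-date check are from SAP 6.8.2. The use of imputed dates is from Protocol 9.5. The screening window is Day -35 to Day -14 from SAP 6.8.1, in which Day -1 is the day before Day 1. The same window follows from Protocol Table 1: Day -28, with a visit window of -7 to +14 days.

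**Step 1: the year-only rule in general.** Let D be first dose and y the recorded onset year.

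Imputed onset = max(D, 1 January of y).

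If y is before the year of D, then 1 January of y is before D, so the maximum is D every time. Applied to 1,000 consecutive first-dose dates with y set to the preceding calendar year, the rule left 0 onsets before first dose.

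**Step 2: a worked case.** Assume first dose on 12 January 2023. Count an onset on the first-dose date as treatment-emergent; the wholly-missing rule relies on the same convention.

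| AE end date | Onset 2022, no end-date check | Onset 2022, with end-date check | Onset December 2022 |
|---|---|---|---|
| none | 12 Jan 2023, TEAE | 12 Jan 2023, TEAE | 1 Dec 2022, not TEAE |
| 1 Feb 2023 | 12 Jan 2023, TEAE | 12 Jan 2023, TEAE | 1 Dec 2022, not TEAE |
| 5 Jan 2023 | 12 Jan 2023, TEAE | 5 Jan 2023, not TEAE | 1 Dec 2022, not TEAE |
| 28 Dec 2022 | 12 Jan 2023, TEAE | 28 Dec 2022, not TEAE | 1 Dec 2022, not TEAE |

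If the end-date check does not cover year-only dates, the last two rows receive an onset after their own end date. If it does, those two are rescued, but events ongoing at first dose or with no end date are still misclassified.

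**Step 3: how often it can arise.** AEs are collected from consent, so an earlier-year onset needs the interval from consent to first dose to span 1 January. With first doses spread evenly over the year, the share is interval / 365:

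- 14 / 365 = 3.8%
- 28 / 365 = 7.7%
- 35 / 365 = 9.6%

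For scale, among the 33 participants in the interim analysis (SAP 6.7.1) this is 33 × 0.038 = 1.3 to 33 × 0.096 = 3.2 people. That is before requiring an AE in the interval, a year-only onset, and an event ongoing or without an end date at first dose.

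**Step 4: the 76-week SAP.** Its TEAE definition (5.2.1) starts at the first ASP0367 dose, while its 6.8.2 refers to the first dose of study drug. For participants randomised to ASP0367 these are the same date, so Step 3 carries over. For participants moving from placebo to ASP0367, section 6.3 of that SAP separates the two terms and uses the OLE first-dose date for first ASP0367. Their reference date in 6.8.2 is therefore most naturally the first double-blind dose. An event with an earlier-year onset would be imputed to that dose, which precedes ASP0367, and would not be a TEAE.

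**The case against.** The strongest reply is that the effect is close to empty. A case needs an AE that starts after consent and within about five weeks of first dose, with only its year recorded although AEs are assessed at every visit, and that is still open at first dose. Clinically relevant abnormalities found at screening go to medical history (Protocol 7.2.3), and nothing in the documents shows that any year-only AE onset exists. All of that stands. It limits the size of the problem but does not make the rule right.

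A second reply is that moving onsets to first dose is conservative for safety. It carries little weight here, because the recorded year already settles the order of events. Protocol 7.3.1 also has an AE whose severity changes relisted with a new onset date, so a pre-dose event that worsens on treatment gets its own on-treatment record.

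Third, the two rules do not contradict each other. They apply to different inputs and can never both govern one record. That is correct: they are inconsistent in approach.

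A reader might also infer two stronger things that the documents do not support.

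- **Placebo-period events counted against ASP0367.** Because a 52-week placebo period almost always contains a 1 January, one might think the 76-week SAP moves many placebo-period events onto the first ASP0367 dose. That needs the first ASP0367 dose as the reference date. Section 6.8.2 does not say so, and the terms in section 6.3 point the other way.
- **Inflated drug-related or special-interest counts.** A treatment-emergent flag alone does not create either. A related TEAE needs the investigator's yes (5.4.1). The cardiac and skeletal-muscle special-interest events also need a troponin, CK, ECG or echocardiogram criterion (6.5.1).

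**Conclusion.** The point holds as a defect in the year-only rule of section 6.8.2 in both SAPs. An AE whose recorded year places its onset before treatment is dated to first dose and classed as treatment-emergent, whereas the month-and-year rule keeps an equivalent event before treatment.

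The effect is small. In the 52-week SAP, and for participants randomised to ASP0367 in the 76-week SAP, about 4% to 10% of participants could meet the calendar condition, and only a year-only onset that is ongoing or has no end date at first dose would then be misclassified. If the end-date check does not reach year-only dates, events that ended before first dose are misclassified too.

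The percentages assume even enrolment over the year and a consent-to-first-dose interval equal to the screening window. The classification assumes that an onset on the first-dose date counts as treatment-emergent. No effect on efficacy arises.

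**What to change.** Add the missing branch to section 6.8.2 of both SAPs:

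> If the onset year is before the year of the first dose of study drug, the imputed onset date is 1 January of the onset year and the AE is not treatment-emergent; otherwise use the later of the first dose and 1 January of the onset year.

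Also state that the end-date check applies to all imputed onset dates, whichever tier produced them.

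This mirrors the month-and-year branch. In the worked case a 2022 onset becomes 1 January 2022 and is not a TEAE for any of the four end dates; a 2023 onset stays at 12 January 2023 and remains a TEAE.

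The edit should not change the reference date. Replacing it with first ASP0367 in the 76-week SAP would reclassify events. Assume placebo from September 2022, OLE from 1 September 2023 and an ongoing AE with onset 2023. The current text gives 1 January 2023, before ASP0367; the replacement would give 1 September 2023 and make it a TEAE.

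The cost is two sentences in each SAP and a line or so of programming. If the SAPs are already final, both provide for changes to be documented in the CSR.
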